
Section	Original Text (Amendment 3.1, 21 December 2016)	Revised Text (Version 4, 10 May 2017)	Justification for Change
	
The propensity score quintile will be then be used as the stratification factor in the stratified log rank test to compare randomized OCA-treated subjects in the ITT population and historical controls (Overall Historical Control Population: both the UK-PBC Group and Global PBC Study Group databases) on the following outcomes:
 
 • Time to hepatocellular carcinoma 	
third-party statistician(s) will be separate and independent from the statistician(s) who will assess the success of matching and perform efficacy analyses.
 
The propensity score quintile will be then be used as the stratification factor in the stratified log rank test to compare randomized OCA-treated subjects in the ITT population and historical controls (Overall Historical Control Population: both the UK-PBC Group and Global PBC Study Group databases) on the following outcomes:
	

Section 13.1.9 Handling of Dropouts or Missing Data
	
Insertion
	
In addition, the same analyses for primary and key secondary endpoints based on ITT and PP populations will be performed to assess robustness of analysis results. During the conduct of the study, the DMC may recommend refining the missing data strategy to better address the observed pattern of missing data, based on blinded monitoring of the data.
	
Clarification of statistical analyses to address missing data.

Section 13.1.11 Examination of Subgroups
	
The primary and secondary efficacy endpoints will be analyzed for subject subgroups (eg, age, sex, and race) based on the ITT population.
 
Insertion
	
The primary and secondary efficacy endpoints will be analyzed for subject subgroups based on the ITT population.
 
The primary efficacy endpoint will also be assessed across the spectrum of PBC disease stage as defined by Rotterdam criteria (Kuiper 2009)
 
 • Early (normal albumin and normal bilirubin) 	
Added per Regulatory Authority request.

Section	Original Text (Amendment 3.1, 21 December 2016)	Revised Text (Version 4, 10 May 2017)	Justification for Change

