
Synopsis, Statistical Methods, Sample Size Justification
 
Section 13.1.2, Determination of Sample Size
	
The following assumptions were used in sample size calculations:
 
 Exponential survival curves, placebo survival estimate of 0.5 at 8 years with a hazard ratio of 0.60, and total study duration of 8 years, allowing for 2 years accrual and 6 years of follow up 
Insertion
 
Based on the randomization ratio, significance level, and assumed hazard ratio, a total of 121 events (both groups combined) will provide 80% power to demonstrate a statistically significant difference between OCA and placebo on time to clinical outcomes.
 
In addition, based on the remaining assumptions stated above, it is estimated that approximately 350 subjects will be enrolled to attain 121 events.
	
The target population is subjects who are at higher risk of liver-related clinical complications. Eligible subjects will have a diagnosis of PBC with bilirubin levels >ULN and ≤5x ULN and/or ALP >3x ULN.
 
The following assumptions were used in sample size calculations:
 
 Exponential survival curves, placebo survival estimate of 0.6 at 8 years with a hazard ratio of 0.60, and total study duration of 10 years (from first subject enrolled), allowing for 4 years of subject accrual and 6 years of follow up. Two interim analyses and one final analysis are planned. The first interim analysis will be performed when 50% of the target events are accrued and the second interim will be performed when 75% of the target events are accrued. A dropout rate of 10% is assumed 
Based on the randomization ratio, significance level, and assumed hazard ratio, a total of 127 events (both groups combined) will provide 80% power to demonstrate a statistically significant difference between OCA and placebo on time to liver-related outcomes, including all-cause mortality.
 
In addition, based on the remaining assumptions stated above, it is estimated that approximately 428 subjects will be enrolled to attain 127 events.
	
Rationale 8
 
Rationale 4
 
Rationale 3

Section	Original Text (Amendment 3, 07 September 2016)	Revised Text (Version 4, 10 May 2017)	Justification for Change

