
Section 12.1.6 Suspected Liver-Related Clinical Outcome Events
	
For liver-related clinical outcome events could also meet the criteria of a SUSAR, which would necessitate unblinding for expedited reporting, please refer to Section 11.1.2.4.
 
The Sponsor will consider the following list of clinical outcome events (MedDRA preferred terms) to be disease related and exempt from expeditious regulatory reporting, but will continue to report them in a non-expeditious manner: death, end-stage liver disease (preferred term: chronic hepatic failure), liver transplant (preferred term: liver transplant), HCC (preferred term: hepatocellular carcinoma), variceal bleeding (preferred term: gastroesophageal variceal haemorrhage), hepatic encephalopathy (preferred
	
Given that the liver-related clinical outcome events may also meet the criteria of a SUSAR, but are considered in aggregate as part of the primary endpoint and the DMC reviews of all safety and efficacy data at least quarterly, the Sponsor will not expeditiously report suspected liver-related clinical outcome events in order to retain the study blind and preserve the integrity of the clinical outcomes endpoint. These events will be selected as a “study event” on the AE CRF and will be submitted for adjudication to the Hepatic Outcomes Committee as described in Section 13.4.
 
The Sponsor will consider the following list of clinical outcome events (MedDRA preferred terms) to be disease related and exempt from expeditious regulatory reporting, but will continue to report them in a nonexpeditious manner: death, end-stage liver disease (preferred term: chronic hepatic failure), liver transplant (preferred term: liver transplant), HCC (preferred term: hepatocellular carcinoma), variceal bleeding (preferred term: gastroesophageal variceal haemorrhage or oesophageal varices
	
Updated to align with modified standard safety procedures and Sponsor standard language.

Section	Original Text (Amendment 3, 07 September 2016)	Revised Text (Version 4, 10 May 2017)	Justification for Change
	term: hepatic encephalopathy), and spontaneous bacterial peritonitis (preferred term: peritonitis bacterial).	haemorrhage), hepatic encephalopathy (preferred term: hepatic encephalopathy), spontaneous bacterial peritonitis (preferred term: peritonitis bacterial), ascites (preferred term: ascites), and histological or clinical progression to cirrhosis (preferred term: hepatic cirrhosis).	

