	Study Group. To evaluate the robustness of the propensity score estimations, additional algorithms and factors may be considered.		

Section 13.1.9 Handling of Dropouts or Missing Data
	
Insertion
	
In addition, the same analyses for primary and key secondary endpoints based on ITT and PP populations will be performed to assess robustness of analysis results. During the conduct of the study, the DMC may recommend refining the missing data strategy to better address the observed pattern of missing data, based on blinded monitoring of the data.
	
Clarification of statistical analyses to address missing data.

Section 13.1.11 Examination of Subgroups
	
The primary and secondary efficacy endpoints will be analyzed for subject subgroups (eg, age, sex, and race) based on the ITT population.
 
Insertion
	
The primary and secondary efficacy endpoints will be analyzed for subject subgroups based on the ITT population.
 
The primary efficacy endpoint will also be assessed across the spectrum of PBC disease stage as defined by Rotterdam criteria (Kuiper 2009)
 
 • Early (normal albumin and normal bilirubin) • Moderate (abnormal albumin or abnormal bilirubin) • Advanced (abnormal albumin and abnormal bilirubin) 
The primary efficacy endpoint will also be assessed for the following clinically relevant subpopulations.
 
 • Monotherapy in patients who are intolerant or non-responsive to UDCA • Elderly patients 
Assuming a strong correlation between biochemistry and clinical outcomes using the
	
Added per Regulatory Authority request.

Section	Original Text (Amendment 3, 07 September 2016)	Revised Text (Version 4, 10 May 2017)	Justification for Change
		
total study population (Section 13.1.5.1) is observed, we will further assess the biochemical improvement in relevant subpopulations as applicable (eg, Rotterdam disease severity and monotherapy) and estimate the reduction in risk of clinical outcomes associated with the biochemical improvement.
 
Additional details regarding statistical methods and subgroup definitions will be provided in the SAP.
	

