
Section 13.1.12 Continuous Monitoring and Interim Analyses
	
Insertion
	
13.1.12 Continuous Monitoring and Interim Analyses
 
Blinded safety reports including the accrual of events, drop outs, and/or loss of subjects to commercially available OCA will be reviewed by the DMC on a regular basis.
 
Two planned interim analyses of the liver-related outcomes will be conducted using the Lan-DeMets O’Brien-Fleming boundaries (Reboussin 2000). Both interim analyses will be pre-specified and will occur after accrual of 50% (64 events) and 75% (96 events) of clinical outcome events, respectively.
 
The DMC will review the available efficacy data in conjunction with detailed safety data and other relevant information to recommend continuation, modification, or cessation (for efficacy) of the study beyond each interim analysis. Modification of the study would not take place without prior agreement with regulatory authorities.
	
Two Interim Analyses have been added to the protocol.

Section 19 List of References
	
Insertion
	
Beuers U, Gershwin M, Gish R, et al. Changing nomenclature for PBC: From
	
Additional relevant references were added.

Section	Original Text (Amendment 3, 07 September 2016)	Revised Text (Version 4, 10 May 2017)	Justification for Change
		
‘cirrhosis’ to ‘cholangitis’. Digestive and Liver Disease. 2015a;47(11):924-6.
 
Beuers U, Gershwin M, Gish R, et al. Changing nomenclature for PBC: From ‘cirrhosis’ to ‘cholangitis’. Gastroenterology. 2015b;149(6):1627-9.
 
Beuers U, Gershwin M, Gish R, et al. Changing nomenclature for PBC: From ‘cirrhosis’ to ‘cholangitis’. Hepatology. 2015c;62(5):1620-2.
 
 
 
	

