
5.7. Summary of Known Potential Risks with OCA
	
Clinical Data In two Phase 2 studies and a Phase 3 study evaluating OCA in the treatment of subjects with PBC, hepatic adverse events were observed in subjects receiving doses of OCA ranging from the maximum approved dose of 10 mg once daily to 50 mg (5 times the highest recommended dose). Recent safety findings in NASH clinical trials include 2 cases of hepatic decompensation reported as SUSARs, 1 of which resulted in death. Both cases involved numerous confounding factors that make evaluation of association with treatment difficult. Details for both events are provided in the Investigator’s Brochure Addendum 1 to Version Number: 16 (31 March 2017), Effective Date: 02 October 2017. The primary AE shown to be related to OCA is pruritus. Pruritus has also been observed in clinical studies with OCA in other indications, as well as in healthy subjects, with the highest frequency observed in subjects with PBC. The incidence and severity of pruritus have
	
Clinical Data In two Phase 2 studies and a Phase 3 study evaluating OCA in the treatment of subjects with PBC, hepatic adverse events, including jaundice, worsening ascites and primary biliary cholangitis flare, were observed in subjects receiving doses of OCA ranging from the maximum approved dose of 10 mg once daily to 50 mg 5 times the highest recommended dose), as early as one month after starting treatment with OCA. In addition, safety findings in NASH clinical trials include 2 cases of hepatic decompensation reported as SUSARs, 1 of which resulted in death. Both cases involved numerous confounding factors that make evaluation of association with treatment difficult. The primary AE shown to be related to OCA is pruritus. Pruritus has also been observed in clinical studies with OCA in other indications, as well as in healthy subjects, with the highest frequency observed in subjects with PBC. The incidence and severity of pruritus have been shown to be dose dependent, but there is no evidence of association with stage or progression of underlying disease. Changes in lipid profiles have also been observed with OCA dosing, including an increase in low density lipoprotein (LDL) cholesterol and a decrease in high-density lipoprotein (HDL) cholesterol. The clinical significance of these lipid findings remains unclear and is being studied further. An independent data monitoring committee (DMC) has performed detailed reviews of individual subject and aggregate data from both the Phase 3 clinical outcomes study in subjects with PBC (Study 747-302) and the Phase 3 pivotal studies in subjects with NASH fibrosis (Study 747-303) and NASH cirrhosis (Study 747-304) on a quarterly basis, in an unblinded fashion, and in
	
Updated the known potential risks of OCA.

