
Section	Original Text (Amendment 5, 04 Jan 2018)	Revised Text (Version 6, 05 Nov 2019)	Justification for Change
	
adjudicated events has accrued. If a subject reaches an outcome event, he or she should continue the regular visit schedule and continue taking investigational product as long as the subject has not met any of the criteria for mandatory interruption of investigational product outlined in Table 7, and the Investigator assesses it as safe. In general, subjects should be strongly encouraged to both stay on investigational product and remain in the study until study termination
		

7.9, Subject Retention
	
A new section was created.
	
The primary objectives for the end of study analysis are to evaluate the effects of OCA compared with placebo on all-cause mortality and liver-related clinical outcomes. The overall study duration is event driven and will be determined by the time required to observe the prespecified adjudicated events for the clinical outcomes’ composite endpoint (Section 7.1). Therefore, it is critical that subjects continue to participate for the duration of the study to enable assessment of clinical outcomes and confirmation of the clinical benefit of OCA in PBC.
 
Subjects may discontinue investigational product during the study; however, these subjects are expected to continue in the study until study termination and every effort will be made by the investigator to discuss subjects’ continuation in the study. Even if a subject is no longer receiving investigational product, if the subject is attending study visits or participating in study follow-up, their information will contribute to the study primary endpoint and the evaluation of clinical benefit of OCA. All information collected in the study during regular study visits and through subjects participating in follow-up will contribute to the evaluation of safety of OCA and the scientific and medical understanding PBC.
 
Investigators should emphasize to subjects the importance of their continuation in the study even after withdrawal of investigational product and discuss with subjects the various options for continued participation in the study:
 
 • Continuing to attend regularly scheduled visits, or 	
A new section was created to provide guidance on the importance of retaining subjects in the study.

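### Section 13.1.9 describes the DMC's missing-data advice as blinded, but this DMC sees comparative results; the risk is small and the fix is cheap

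*Protocol*

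**What the plan says.** The body of Section 13 is not in the part of the protocol shown. The wording comes from the revised-text columns of the Version 4 change logs (Appendices H and I). The Version 5 and Version 6 logs list no change to 13.1.9, though they do not itemise minor edits.

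- **13.1.9, missing data:** "the DMC may recommend refining the missing data strategy to better address the observed pattern of missing data, based on blinded monitoring of the data". The sentence before it concerns ITT and per-protocol analyses of the primary and key secondary endpoints as a check of robustness.
- **13.1.12, routine reports:** "Blinded safety reports including the accrual of events, drop outs, and/or loss of subjects to commercially available OCA will be reviewed by the DMC", at regular intervals.
- **13.1.12, interim analyses:** at 64 and 96 events, against Lan-DeMets O'Brien-Fleming boundaries, "The DMC will review the available efficacy data in conjunction with detailed safety data" and may recommend stopping for efficacy.
- **12.1.6:** potential SUSARs among outcome events are not expedited, partly because of "the DMC reviews of all safety and efficacy data at least quarterly".
- **5.7 (Version 6):** the DMC has reviewed individual and aggregate data, with this study named, "on a quarterly basis, in an unblinded fashion" and in sessions closed to the sponsor.
- **Safeguards:** 13.1.8 requires prior regulatory agreement before the planned primary analysis is revised. 13.1.12 requires the same before the study is modified. Section 13 has the SAP approved before the first interim analysis.

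**The concern.** Refining a missing-data strategy during a trial is acceptable when those who propose it cannot know which option favours which arm. Section 13.1.9 claims that protection but assigns the task to the one body that the rest of the protocol describes as seeing results by arm. A pooled report blinds the report. It does not blind members who already know the comparison. The sentence has no cut-off, so it also covers the period after an interim look.

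What is at stake is mostly credibility. If the handling of lost or withdrawn subjects changed after 64 events on this committee's advice, a critic could say that the change followed the results, and the plan could not show otherwise. A secondary question is whether type I error could move.

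**Working it through.** **Step 1: does the DMC see comparative data?** The interim design can be reproduced. Inputs from 13.1.2 and 13.1.12 are HR 0.60, 1:1 allocation, 80% power, 127 events, and looks at 64 and 96 events. Alpha is not stated in the part shown. I assume two-sided 0.05.

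- Fixed design: 4(1.960 + 0.842)² / (ln 0.60)² = 4 × 7.85 / 0.261 ≈ 120.3, so 121 events. This matches the target before interim analyses were added and supports the assumed alpha.
- Information at the looks: 64/127 = 0.504 and 96/127 = 0.756.
- Boundaries: z = 2.949, 2.348 and 2.016. Power at 127 events is 81.3%, consistent with the stated 80%.
- Hazard ratio at each interim boundary, exp(−2z/√d): exp(−2 × 2.949/8) ≈ 0.48 and exp(−2 × 2.348/9.80) ≈ 0.62.

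A committee cannot judge these boundaries without the comparison between arms. Section 13.1.12 does not use the words by arm, but the boundaries imply it, and 5.7 (Version 6) states unblinded quarterly review directly.

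**Step 2: who is open to a changed rule?** Under 7.9 and 9.7.15 (Version 6), subjects off product who remain in visits or follow-up still count: "their information will contribute to the study primary endpoint". That largely leaves subjects truly lost or withdrawn. In 13.1.2, "A dropout rate of 10% is assumed". Read as true loss, 0.10 × 428 ≈ 43 subjects.

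**Step 3: effect on error.** Trials were simulated under HR 1 with 428 subjects, uniform 4-year accrual and hazard −ln(0.6)/8 = 0.0639 per year in both arms. Exponential loss was set to give 43 losses by the 127th event. The log-rank test was run at 64, 96 and 127 events with the boundaries above. The worst-case assumption is that a committee knowing the arm results always picks the option with the better z, and that its choice is always adopted.

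| Options to choose between | No choice | Choice at 64 events | Choice at 96 events |
|---|---|---|---|
| Censor, or count each loss as an event (200,000 trials, SE 0.0004) | 0.0250 | 0.0338 | 0.0342 |
| Censor, or multiple imputation at the placebo hazard (80,000 trials, SE 0.0006) | 0.0261 | 0.0254 | 0.0260 |
| Count or censor follow-up after stopping product, about 20 stops (100,000 trials) | 0.0244 | 0.0264 | 0.0268 |

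- For the first pair, a blinded choice from the pooled loss count gives 0.0254.
- A separate run of the first pair (150,000 trials) gave 0.024 rising to 0.033.
- With loss set at 10% by year 10 instead, about 21 subjects are lost and the error for the first pair is about 0.031 (120,000 trials).
- The final z-values of the two options correlate 0.865 in the first pair and 0.993 in the second, which is why the second gives nothing to exploit.
- The third row is largely settled by 7.9 and 9.7.15, which count that follow-up.
- If only robustness analyses are refined, the primary error does not change.

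**The case against.** **The blinding phrase describes the data, not the committee.** Section 13.1.12 supplies blinded pooled reports, and the committee's charter, which is not shown, may confine this task to them. On that reading there is no flat contradiction in the text. That is fair, but it does not answer the point. The members also hold the comparative results, and the part shown names no separate blinded group for this task.

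**The sentence may concern only sensitivity analyses.** Its neighbour is about robustness, and the stated reason for the insertion is clarification. This is a natural reading, and under it the primary error is untouched. The wording is not limited to those analyses, however.

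**A reader might infer that the DMC can change the primary analysis on its own, or that type I error is materially at risk.** The documents do not support either. The DMC only recommends, and 13.1.8 and 13.1.12 require prior regulatory agreement for such changes. The SAP fixes the baseline rule before the first interim analysis, although the quarterly unblinded reviews in 5.7 weaken that protection. The figure of 0.034 also requires an implausible pair of options, a committee that always favours the sponsor, and automatic adoption. These safeguards limit the harm. They do not make the recommendation blinded.

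**The source is indirect.** The 13.1.9 text is Version 4 wording set beside Version 6 text in 5.7. This stands as a caveat, but 12.1.6 and 13.1.12 are themselves Version 4 text and carry the point without 5.7.

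**Conclusion.** The point holds in a narrow form. The protocol gives the proposing role to a committee that knows the comparative results, so advice it offers under 13.1.9 cannot properly be called blinded.

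The size is small. One-sided error moves by about 0.009 (0.025 to 0.034) under the extreme assumptions above, by less if fewer subjects are truly lost, and not detectably for censoring against multiple imputation. This rests on two-sided 0.05, on the 10% dropout read as true loss, and on 13.1.9 being unchanged since Version 4. The case rests on defensibility rather than on error control. It is a cheap improvement of low priority. It does not touch the DMC's harm monitoring or stopping role.

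**What to change.** In 13.1.9, replace the DMC as proposer with statisticians blinded to treatment arm and to interim results, who may propose refinements from pooled data. They can draw on the blinded quarterly evaluation of event rate, recruitment and retention already planned in 13.1.2.1.

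Add two conditions. Each change is documented in a dated SAP amendment before unblinding. Any change affecting the primary analysis stays subject to the prior regulatory agreement in 13.1.8. The second condition matters because, without it, an advisory step by an independent body would become an unchecked sponsor power.

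Optionally, state in 13.1.12 that the pooled reports on events, drop-outs and commercial OCA also go to that team, separately from the DMC's closed sessions.

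The cost is a short rewording, and the DMC loses the right to propose missing-data changes. Mid-study refinement remains possible, and the pooled data should already exist.
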